### 12.2. ADDITIONAL PK ANALYSIS

The following additional PK analysis will be performed:

 Blood concentration of clevidipine and its carboxylic acid metabolite (M1) over time

Blood concentration of clevidipine and M1 will be plotted over time by cohort. PK modeling of blood concentration of clevidipine versus any or all of weight, height, body surface area, age, sex or ethnicity may be explored when appropriate.

 Relationship between dose and blood concentration of clevidipine for overall and by cohort

Blood concentration will be plotted over dose for overall and by cohort. Dose proportionality will be explored. PK modeling of blood concentration of clevidipine versus dose plus any or all of weight, height, body surface area, age, sex or ethnicity may

be performed to explore the potential effect of covariance on the dose-concentration relationship.

 Relationship between first on-study blood concentration of clevidipine and body weight

First on-study blood concentration of clevidipine will be plotted over body weight. This might be done by age, sex or ethnicity.

We may also perform analysis to explore the following:

- Potential effect of body weight, height, body surface area, age, sex, ethnicity or dose on total clearance (CL)
- Potential effect of body weight, body surface area, age, sex ethnicity or dose on volume of distribution (Vss)

### 12.3. PK/PD RELATIONSHIP

The following analyses will be performed for PK/PD relationship:

• Relationship between change and/or percent change from baseline in SBP and first on-study blood concentration of clevidipine for overall and by cohort

Change and/or percent change from baseline in SBP will be plotted over first on-study blood concentration for overall and by cohort. Appropriate PK/PD modeling may be explored whenever necessary.

 Relationship between dose and change or percent change from baseline in SBP for overall and by cohort

Change and/or percent change from baseline in SBP will be plotted over dose for overall and by cohort. Appropriate PK/PD modeling may be explored whenever necessary.

• Relationship between blood concentration of clevidipine and change or percent change from baseline in SBP will be explored for overall and by cohort

Change and/or percent change from baseline in SBP will be plotted over blood concentration for overall and by cohort. Appropriate PK/PD modeling may be explored whenever necessary.

### 13. SUBGROUP ANALYSES

Subgroup analysis in patients with and without pre-existing hypertension will be performed for efficacy and safety endpoints for the cohorts with reasonable number of patients in each subgroup to warrant feasible analysis.

Pre-existing hypertension for children of 1 to 17 years old will be defined as the average of SBP or DBP that is ≥95th percentile for gender, age and height on at least 3 separate occasions on or before baseline according to the definition specified in "The Fourth Report on the Treatment of High Blood Pressure in Children and Adolescents" [NIH Publication, 2005]. The pre-existing hypertension for neonates will be defined according to the definition specified in "Neonatal hypertension: diagnosis and management" [Flynn, 2000].

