4.3. EXCLUSION CRITERIA

Patients will be excluded if they present with any of the following exclusion criteria:

- 1. Administration of an IV or oral antihypertensive agent within 2 hours prior to study drug administration
- 2. Congenital heart disease described as single ventricle
- 3. Evidence of liver failure, severe liver disease, pulmonary disease (e.g., uncontrolled asthma), hyperlipidemia, lipoid nephrosis, lipid dysfunction or acute pancreatitis
- 4. Allergy to soya bean oil or egg lecithin
- 5. Known to be intolerant to calcium channel blockers
- 6. Hemophilia or blood coagulation disorders
- 7. Any serious medical condition which, in the opinion of the investigator, is likely to interfere with study procedures
- 8. Clinically significant abnormal physical findings at the screening evaluation
- 9. Any serious surgical or medical condition which, in the opinion of the investigator, is likely to interfere with study procedures or with the pharmacokinetics or pharmacodynamics of the study drug
- 10. Patient is terminally ill (death likely to occur within 48 hours)

- 11. Use of methylphenidate, calcium channel blockers, aripiprazole and other atypical anti-psychotics and antihypertensive used for BP control within 2 hours prior to study drug initiation
- 12. Positive serum or urine pregnancy test for any female of childbearing potential
- 13. Participation in other clinical research studies involving the evaluation of other investigational drugs or devices within 30 days of enrollment
- 14. Patients who, for any reason, are deemed by the investigator to be inappropriate for this study
- 15. Patient is a relative of the investigator or his/her deputy, research assistant, pharmacist, study coordinator, other staff directly involved in the conduct of the study

Patients excluded for any of the above reasons may be re-screened for participation at any time if the exclusion characteristic has changed.

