6. SCHEDULE AND SEQUENCE OF PROCEDURES

The Schedule of Assessments (Section 6.1 and Table 1) summarizes the study tests and procedures by time point. This study is comprised of three consecutive periods: a screening period, a treatment period, and a follow up period. The maximum duration of a patient's participation on study is approximately 18 days (screening up to 7 days, study drug administration up to 4 days and follow-up to 7 days).

The screening period begins from the time patients are consented for elective surgery to immediately prior to administration of study drug. The screening period consists of obtaining informed consent, confirming patient eligibility and collecting baseline assessments. During this period, a medical history (including all medications taken) and a physical examination (including height, length and weight) will be performed. Laboratory assessments (Section 6.3) including a pregnancy test for girls of childbearing potential will be performed. HR and BP measurements will be performed. With the exception of the pregnancy test, results of the laboratory tests are not required prior to administering study drug.

Prior to study drug administration, HR and BP measurements will be recorded. These will serve as the baseline HR and BP. Once a patient is deemed eligible a prespecified SBP target range must be identified prior to initiation of study drug treatment and recorded in the patient's medical record. The target range will later be entered into the eCRF.

The study drug infusion will commence following:

- Establishment of stable anesthetic condition (minimal change in anesthetic drug concentration and dose)
- Observation of stable vital signs following skin incision

The treatment period occurs from initiation of study drug up to 96 hours. This period is split into 3 phases for study drug administration. Initial dosing phase from 0 to 1.5 minutes; maintenance phase from > 1.5 to 30 minutes up to 96 hours and study drug transition phase defined as the transition and/or cessation of infusion.

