### 4. GENERAL STATISTICAL METHODOLOGY

All statistical analyses and summary information will be generated according to this statistical analysis plan (SAP). Any deviations from this SAP will be documented in the clinical study report (CSR).

Patient disposition, demographic and background characteristics will be presented for the safety, ITT and PK/PD populations. Unless otherwise specified, all efficacy analyses will be performed using the ITT population, all safety analyses will be performed using the safety population and all PK/PD analyses will be performed using the PK/PD population.

Continuous variables will be summarized using descriptive statistics including the number of patients reflected in the calculation (n), mean, standard deviation (SD), median, interquartile range (Q1 and Q3), minimum (min), and maximum (max). Frequencies and percentages will be displayed for categorical variables.

Because of the descriptive nature of this study, no formal statistical hypothesis testing will be performed. However, p-values and/or two-tailed 95% confidence intervals may be generated to demonstrate the strength of the findings whenever appropriate.

All data will be summarized for overall and by age cohort. Data listings will be provided for all data collected in the eCRF.

Unless otherwise specified for repeat pre-baseline assessments, the results from the final assessment made before or at the start of study medication will be used as baseline. If post-baseline assessments are repeated or unscheduled, the non-missing values from the first assessment will be used for generating summary statistics.

Unless otherwise specified (eg, in Section 8), missing data will not be imputed and will be excluded from the associated analysis.

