### 6. DEMOGRAPHICS AND BASELINE CHARACTERISTICS

Demographics including sex, age, ethnicity, height, weight, and BMI, baseline characteristics including blood pressure and heart rate, relevant medical history, as well as relevant past surgical/interventional procedure will be summarized with descriptive statistics for all populations (safety, ITT and PK/PD).

Listings of demographics, baseline characteristics, medical history and surgical/interventional procedures will be presented for each patient, including those who are enrolled but not treated with the study medication.

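### The SAP 13 rule for pre-existing hypertension at ages 1 to 17 ignores collected history and treatment, and does not bar blood pressure readings taken during surgery

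*SAP*

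**What the plan says.** SAP 13 plans efficacy and safety summaries in patients with and without pre-existing hypertension, "for the cohorts with reasonable number of patients in each subgroup to warrant feasible analysis". For ages 1 to 17 the label depends on average systolic or diastolic pressure at or above the 95th "percentile for gender, age and height on at least 3 separate occasions on or before baseline", following a cited national report. For the youngest patients it says only: "The pre-existing hypertension for neonates will be defined according to the definition specified in" a cited paper.

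Other sections determine which readings can enter the rule:

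- SAP 4, on repeated pre-baseline assessments: "the results from the final assessment made before or at the start of study medication will be used as baseline".
- Protocol 6 starts the infusion only after a stable anesthetic state and "Observation of stable vital signs following skin incision".
- Protocol 4.3 excludes "Administration of an IV or oral antihypertensive agent within 2 hours prior to study drug administration". Earlier antihypertensive treatment is not excluded.
- Protocol 6 collects at screening "a medical history (including all medications taken) and a physical examination". SAP 6 summarizes "baseline characteristics including blood pressure and heart rate, relevant medical history", and SAP 9 codes and summarizes prior medications. SAP 13 uses none of this.

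**The concern.** Pre-existing hypertension is a condition the child brings to the operation. A rule built only on readings up to the start of study drug can get it wrong in two directions. It can miss a child whose hypertension is known but controlled by treatment, and it can count pressure raised by the operation itself. Protocol 1.1 attributes perioperative rises mainly to sympathetic activation under surgical stress, and SAP 8 records pre-existing and intra-operative hypertension as different reasons for starting drug. The SAP 13 rule can mix the two.

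At stake is the meaning of the one subgroup comparison named in the exploratory objective (Protocol 2.3, SAP 2.3). If treated hypertensive children sit in the comparison group, or intra-operative hypertension sits in the index group, the two columns do not show what their titles say. Deciding which readings count after the data are seen would also let the classification follow the results.

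**Working it through.** The plan gives no figure to reproduce here. The check sets the rule beside the measurement schedule.

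**Step 1. Scheduled pre-drug time points**

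| Time point | Source | Timing |
|---|---|---|
| Screening | Protocol 3.2, 6.1, 7.2.1.1 | day -7 to 0; arterial catheter specified |
| With PK Sample 1 | Protocol 6.3 | up to 30 minutes before drug |
| Baseline set (60, 45, 30, 0 seconds) | Protocol 6.1 footnote 3, 7.2.1.2 | last minute before drug |

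Count: 1 + 1 + 1 = 3 time points, or 1 + 1 + 4 = 6 single readings if screening gives one. The screening count is inferred: Protocol 6 gives no number, and the day -7 to 0 list in Protocol 6.3 omits blood pressure.

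**Step 2. Compare with the rule**

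- Required occasions: 3. Scheduled: about 3. Spare: 3 - 3 = 0.
- Two of the three fall within 30 minutes of drug start. Given the start condition in Protocol 6, they are normally after induction and incision.
- If readings after induction are left out, normally 1 remains (screening), so 3 - 1 = 2 occasions would have to come from the medical record. Neither document asks for them.

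**Step 3. Apply the rule to two children**

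*Treated and controlled.* The last antihypertensive dose was more than 2 hours before study drug, and the screening pressure is normal. If every occasion must qualify, at most 3 - 1 = 2 scheduled occasions are high, which is below 3. The label is 'without', whatever the medical history says.

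*No history, pressure high at surgery.* SAP 4 places the peri-infusion readings within 'on or before baseline', and SAP 13 does not remove them. If the PK Sample 1 reading and the last-minute set count as separate occasions, they supply 2 of the 3 needed. If the screening reading by arterial catheter is also taken in the operative session, all 3 can be operative. A normal screening value before surgery would block the label on this reading.

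**Step 4. The other reading of the rule**

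The sentence can also mean an average taken over at least three occasions. One normal value then need not fail the rule, and operative readings carry 2 of 3 values. The treated child could be labelled 'with', but because of operative pressure rather than the known diagnosis. Both faults in the wording remain.

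**Step 5. How many patients come under the rule**

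Cohorts 1 and 2 supply 20 + 20 = 40. Cohort 3 (20 patients) runs from 28 days to under 24 months. The share below 1 year, assuming evenly spread ages, is (365.25 - 28) / (730.5 - 28) = 337.25 / 702.5 = 0.480. That is 9.6 patients below 1 year and 20 - 9.6 = 10.4 at or above it. Under the rule: 40 + 10.4 = 50.4 of 80. The 9.6 (9.6 / 80 = 12%) have no rule in the SAP's own words. This is a secondary gap in detail.

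**The case against.** Several points against the concern stand and limit it.

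- SAP 13 adopts definitions from a cited report and a cited paper. These may say what a separate occasion is, how treated children are handled, and what ages the neonatal definition covers. Neither can be checked here, so the faults are faults of the SAP wording. A reader might infer that infants from 28 days to under 1 year have no definition at all; the documents support only that SAP 13 states none.
- A reader might infer that exactly three occasions exist and that all three must be high. The schedule does not give a screening count, the word 'average' allows the other reading, and earlier chart readings are not barred.
- A reader might infer that children will be labelled hypertensive from intra-operative readings alone. That requires the screening reading to fall in the operative session and two time points within 30 minutes to count as separate occasions, which strains the ordinary meaning. SAP 8 also allows for drug started before surgery or for post-surgical hypertension, so these readings are not always intra-operative.
- History, prior medications and the reason for starting drug are tabulated or listed, so a mislabelled treated child could be found. That helps a careful reader of the listings but does not correct the subgroup tables.

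What remains: the wording gives history and treatment no role, and it does not exclude operative readings.

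**Conclusion.** The concern holds in this limited form, and it is minor. As worded, SAP 13 puts a child with known, treated and controlled hypertension in the 'without' group, and it allows pressure measured after induction and incision to count as pre-existing. About 50 of 80 planned patients come under the rule, assuming evenly spread ages in cohort 3. How many would be mislabelled cannot be derived: the documents give no number of treated hypertensive children, no timing for arterial line placement, and no rule for counting occasions.

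A reader might infer damage to the main results. The documents do not support that. The subgroup analysis is exploratory and descriptive, and runs only where numbers allow. The label does not enter the primary endpoints, the change-from-baseline summaries or the DSMB reviews.

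**What to change.** Edit SAP 13 only.

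1. **With pre-existing hypertension:** hypertension in the medical history; or prior antihypertensive treatment in a patient whose history or recorded reason for starting study drug is pre-existing hypertension; or at least 3 separate qualifying blood pressure occasions before induction of anesthesia.
2. **Without known pre-existing hypertension:** all other patients.
3. State that readings after induction do not count.
4. As a secondary clarification, name the rule for 28 days to under 1 year.

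The condition on prior treatment is needed because such drugs have other uses (Protocol 5.2.3 permits ACE inhibitors for volume overload), and no section says that the indication for prior medication is recorded. The second group should not require a normal pre-induction reading: screening pressure is specified by arterial catheter, so many children might have none and become unclassifiable.

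Cost: one paragraph, using data already collected, with no new measurement and no protocol change. The downside is that some undiagnosed, untreated hypertensive children stay in the 'without known' group, and the 'with' group rests mainly on history. The word 'known' in the label makes that limit visible.

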### 14. OTHER/EXPLORATORY ANALYSIS

### 14.1. SURGICAL PROCEDURE

Surgery related parameters will be analyzed in this study including:

- Type of surgery
- Pump used for cardiac surgery (yes or no)
- Duration of surgery (initial incision to last suture placed)
- Duration of time on pump for cardiac surgery

Descriptive statistics for each of the above endpoints will be provided by treatment group whenever appropriate. Patient data listings will also be provided.

### 14.2. TARGET SBP RANGE

Prior to enrollment, the investigator predetermines a patient-specific SBP target range for the desired BP reduction. The pre-specified SBP target range cannot be changed for the first 30 minutes of treatment and the difference between upper and lower limits of the specified target SBP range should be no less than 20 mmHg and no more than 40 mmHg. After completing the initial 30 minutes of treatment the SBP target range can be changed as needed.

Initial target SBP range, new target SBP range along with the SBP, HR values at the time the range change was initiated will be summarized for overall and by age cohort.

### 15. INTERIM ANALYSIS

Following completion of each cohort, the DSMB will review both safety and dosing data provided by the Sponsor and make safety and dosing recommendations to the Sponsor according to the DSMB charter prior to enrolling the next cohort. DSMB review of each completed cohort will be required before proceeding to the next cohort to determine if it is appropriate to proceed with enrollment of subsequent cohorts and whether an adjustment in dosing scheme is required.

In addition, the Sponsor will perform an analysis based on the number of patients reaching TBPR within first 30 minutes of study drug infusion to assess the precision of the efficacy findings at the end of each cohort to ensure that sample size for the following cohort is sufficient based on clinical judgement.

### 16. SAMPLE SIZE CONSIDERATIONS

The total sample size of 80 evaluable patients is primarily based on clinical judgment to provide adequate precision of the findings for this non-comparative study. For example, assuming that 90% of patients will achieve the initial target SBP range within the first 30 minutes of infusion, a sample size of 80 patients can provide a 95% confidence interval with a precision of  $\pm 6.6\%$ . This precision will become  $\pm 7.8\%$  if 85% of patients are assumed to achieve the initial target SBP range. The precision will be assessed at the end of each cohort and sample size for the next cohort may be adjusted.

Approximately 10-20 patients per pediatric age group are considered adequate to assess the PK/PD model, based on prior clinical experience in adults.

### 17. COMPUTER METHODS

Statistical analyses will be performed using Statistical Analysis System (SAS) (version 9.0 or later version).

### 18. CHANGES TO ANALYSES SPECIFIED IN THE PROTOCOL

In Protocol Section 10.3.3.3, it was stated to analyze vital signs at each collection time point. In this study, the only vital signs that are collected are SBP, DBP and HR which are already analyzed as individual efficacy endpoint hence there is no additional analysis on vital signs performed.

### 20. APPENDIX

#### 20.1. TIME WINDOWS

### 20.1.1. Visit windows for hemodynamic data (SBP, DBP and HR)

Hemodynamic data (SBP, DBP and HR) will be presented at every 1.5 minutes within 30 minutes of study drug infusion, at every 30 minutes for the next 3 hours, at every hour thereafter till the cessation of infusion and over 12 hours post study treatment. The time window is 30 seconds for 1.5 minutes presentation, 10 minutes for every 30 minutes presentation and 30 minutes for hourly presentation.

### 20.1.2. Visit windows for laboratory parameters

The following are the time windows (in hours) used for the summary tables of laboratory parameters during the study drug infusion.

>0 to <36 for 24 ≥36 to <60 for 48 ≥60 to <84 for 72 >84 to <106 for 96

The following are the windows used for the data measured post the cessation of study drug infusion.

 $\geq$ 1 h post-infusion to  $\leq$ 5 h post-infusion for 4 hours post-infusion

For example, if there is no 48-h measurement, the data measured in the time window between 36 h and 60 h will be considered. The values measured closest to 48 h in the window will be considered as the 48-hrs. value. If two values are both equally close to 48 h in the window, the one measured in the earlier time will be used for the analysis. The assessment at 48-h will be considered missing if there are no assessments in the time window from 36 h to 60 h

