3.3. PRIMARY ENDPOINT(S)

The primary endpoint(s) of this trial are:

- Median time and dose to attain the initial prespecified target SBP range (minimum of 20 mmHg and a maximum of 40 mmHg apart) during the first 30 minutes of clevidipine infusion
- Percentage of patients achieving the initial prespecified target SBP range during the first 30 minutes of clevidipine infusion
- Pharmacokinetic variables (half-life, area under the curve [AUC], volume of distribution, clearance) established by sparse population methodology
- Pharmacodynamic variables (relationship between change from baseline in SBP vs. blood concentration and infusion rate)
- Safety of a prolonged infusion of clevidipine (up to 96 hours) assessed according to clinical laboratory parameters, adverse events and serious adverse events (SAEs) will be assessed from time of consent through 7 days following termination of study drug infusion

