- BP and HR
 - every 10 minutes for the next 1 hour
 - every 30 minutes for the next 2 hours
 - once every hour until study drug is terminated (up to 96 hours)
 - If a dose adjustment is indicated, BP and HR should be recorded just prior to each study drug dose change as well as every 1.5 minutes for 15 minutes after the dose adjustment.
- PK Sample 5: only taken if transition to an additional antihypertensive is desired and concurrent administration at any time >30 minutes and up to 96 hours (taken in the order below)
 - BP and HR
 - PK Sample 5 (as applicable): taken immediately after BP and HR and before beginning administration of an additional antihypertensive agent
 - BP and HR, taken as instructed above
 - BP and HR to continue as instructed above
- Serum chemistry (Section 6.3) every 24 hours (+ 1 hour) from initiation of study drug infusion (up to 96 hours) or at the termination of study drug infusion if study drug is administered for less than the 24 hours
 - Concomitant medications
- AE(s) and SAE(s)

All assessments above (except PK) should be performed again if clevidipine is restarted for any reason.

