### 11.2.2. Laboratory analysis

Descriptive statistics for the values of serum chemistry as well as relative and percent changes from baseline will be summarized by time point: baseline (screening), every 24 hours during study drug administration (or at the termination of study drug infusion if less than the 24 hours timepoint), and at 4 hours after termination of study drug infusion. Values for each hematology parameter will be presented only at screening.

Values of laboratory tests are considered potentially clinically significant (PCS) if they meet the PCS criteria listed in Table 3. The number (percentage) of patients with post-baseline PCS values who do not have PCS values at baseline will be analyzed for the safety population. For calculation of the percentages, the denominator is based on the number of patients with non-PCS baseline values and at least one post-baseline assessment for the laboratory parameter being analyzed. The numerator is based on patients from the denominator who had at least one post-baseline PCS value for the laboratory parameter being analyzed. A supportive listing of patients with all PCS values will be provided including the patient number, age, gender, treatment time. Both raw and standardized pre-baseline, baseline, and post-baseline values and normal ranges will be in the listing, along with the standardized abnormality flag.

Table 3: Criteria for Potentially Clinically Significant Abnormal Laboratory
Tests

Parameter	Low Limit	High Limit					
Serum Chemistry							
Serum Creatinine, mg/dL	_	≥2 mg/dL					
Triglycerides, mg/dL	_	≥300 mg/dL					
Lipase, U/L	_	≥3 × ULN					
Total Cholesterol, mg/dL	_	≥300 mg/dL					
HDL, mg/dL	_	≤20 mg/dL					
LDL, mg/dL	_	≥200 mg/dL					
VLDL, mg/dL	_	≥100 mg/dL					
Alanine Transaminase (ALT/SGPT), U/L	_	≥3 × ULN					
Aspartate Transaminase (AST/SGOT), U/L	_	≥3 × ULN					
Total Bilirubin, mg/dL	_	≥1.5 × ULN					
Lactate Dehydrogenase (LDH)	_	≥3 × ULN					
Blood Urea Nitrogen (BUN), mg/dL	_	≥1.5 × ULN					
Electrolytes	Electrolytes						
Sodium, mg/L	≤0.9 × LLN	≥1.1 × ULN					
Potassium, mg/L	≤0.9 × LLN	≥1.1 × ULN					
Calcium, mg/dL	≤0.9 × LLN	≥1.1 × ULN					
Magnesium	≤0.9 × LLN	≥1.1 × ULN					

LLN: Lower limit of the standard reference (normal) range.

ULN: Upper limit of the standard reference (normal) range.

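### The SAP's 24-hour chemistry row accepts any on-infusion value from just above 0 to under 36 h, so it can average very short and day-long exposures under one label

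*SAP*

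**What the plan says.** - **Windows.** SAP 20.1.2 lists the windows "used for the summary tables of laboratory parameters during the study drug infusion". The first is ">0 to <36 for 24" and the next is "≥36 to <60 for 48". The 72-hour window runs from 60 to under 84 h, and the 96-hour window from above 84 to under 106 h.
- **Choice among several values.** The rule is given by example: "The values measured closest to 48 h in the window will be considered as the 48-hrs. value".
- **Sampling.** Protocol 6.5.2 schedules serum chemistry every 24 h from the start of infusion, "or at the termination of study drug infusion if study drug is administered for less than the 24 hours". SAP 11.2 repeats this.
- **Summary time point.** SAP 11.2.2 defines the on-treatment time point as each 24 h of administration, "or at the termination of study drug infusion if less than the 24 hours timepoint". The 24-hour value and the early-termination value thus share one time point.
- **Purpose.** Protocol 3.3 lists among the primary endpoints "Safety of a prolonged infusion of clevidipine (up to 96 hours) assessed according to clinical laboratory parameters".
- **Breakdown.** SAP Section 4 summarises data overall and by age cohort. Infusion duration and total dose are derived in SAP Section 8 as exposure variables. No laboratory table is split by either.

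**The concern.** A row labelled 24 h will be read as the state of the patients after about a day of drug. Under this window it also holds patients whose only on-treatment sample came at the end of a much shorter infusion. The trial expects such patients: the synopsis sets a minimum exposure of 30 minutes, and eligibility asks only that at least 30 minutes of therapy be anticipated.

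The protocol itself gives reason to care about duration. Section 1.2.3 describes the lipid content of the emulsion and says that hepatic and pancreatic chemistry is monitored because of it. Section 1.2.1 attributes most animal toxicity findings to the lipid in the formulation and says that most were related to dose, duration of treatment, or both. If laboratory effects build up with infusion time, averaging short and long exposures pulls the mean in this row towards the short-exposure value. At stake is how accurately one row describes change after about 24 h, within an analysis that serves a primary safety endpoint.

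**Working it through.** The plan gives no figure of its own on this point. Its only design calculation concerns the precision of the target-range response rate and has no bearing here.

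**1. Window geometry (limits from SAP 20.1.2).** Distance below = label minus lower limit; distance above = upper limit minus label.

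| Row | Window (h) | Below | Above |
|---|---|---|---|
| 24 h | >0 to <36 | 24 − 0 = 24 | 36 − 24 = 12 |
| 48 h | 36 to <60 | 48 − 36 = 12 | 60 − 48 = 12 |
| 72 h | 60 to <84 | 72 − 60 = 12 | 84 − 72 = 12 |
| 96 h | >84 to <106 | 96 − 84 = 12 | 106 − 96 = 10 |

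Only the 24-hour window reaches back to the start of drug.

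**2. Do short infusions enter it?** Yes. The termination sample of an infusion under 24 h is an on-infusion value taken after time 0. It has no other row, because the post-infusion window opens 1 h after the end of infusion.

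**3. Does the closest-value rule keep them out?** No. Barring a restart, a patient infused for under 24 h has one scheduled on-infusion value, so there is nothing closer to 24 h to choose.

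**4. Spread of exposure in the row.**
- A termination sample after 0.5 h reflects 0.5/24 = 2.1% of a 24-hour infusion time; after 4 h, 4/24 = 16.7%; after 6 h, 6/24 = 25%.
- The window allows a ratio of up to 36/0.5 = 72.
- If every sample is on schedule, the latest is at 25 h (24 h plus the 1 h allowance), and the ratio is 25/0.5 = 50.

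**5. Effect on the mean (illustration only).** Let D be the true mean change at about 24 h, s the share of the row that comes from short infusions, and f the fraction of D already present in them. Then

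row mean / D = (1 − s) + s × f.

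The documents supply neither s nor f; both are assumed. For example, s = 0.75 and f = 0.25 give 0.25 + 0.1875 = 0.4375.

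| s | f = 0 | f = 0.25 |
|---|---|---|
| 25% | 75% | 81.25% |
| 50% | 50% | 62.5% |
| 75% | 25% | 43.75% |
| 90% | 10% | 32.5% |

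With f = 0 the row shows the true change multiplied by the share of patients actually infused for about 24 h. The formula has two groups only; real durations would fill the range between them.

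**The case against.** Most of the case against limits the scope of the point, and those limits stand.

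- **One row only.** A reader might infer that the whole laboratory assessment of prolonged infusion is diluted. The documents do not support that. On-infusion values in the 48-, 72- and 96-hour rows can come only from patients infused for at least 36 h, at least 60 h and more than 84 h respectively.
- **Abnormal values are counted elsewhere.** Incidence of potentially clinically significant values under SAP 11.2.2 uses any post-baseline value, whatever its window. Its denominator also ignores exposure, but that is a separate matter, which changing this window would not alter.
- **The row would not hide everything.** A reader might also infer that the row must look flat whatever happens at 24 h. SAP Section 4 requires SD, quartiles, minimum and maximum, so large values would still appear in the maximum and SD, and in the upper quartile if frequent enough. The listing of significant values gives treatment time.
- **The pooling is disclosed.** SAP 11.2.2 says openly that termination samples are included. This stands as to transparency. It does not make the 24-hour label accurate, and a listing restricted to patients with significant values cannot recover the mean change at 24 h.
- **Direction is not certain.** Baseline chemistry is the screening sample, up to 7 days earlier, and surgery lies between. Values may move after a short infusion for reasons unrelated to the drug. If f exceeded 1, the row would overstate the 24-hour change.
- **No decision rests on this mean.** The study is descriptive, with no formal testing.

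What remains is that no planned laboratory summary separates short from day-long exposure, and that this window merges them under one label.

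**Conclusion.** The point holds for the 24-hour summary row. By its stated limits and the termination-sample rule, that row can mix exposures from about 30 minutes to nearly 36 h, and its mean may misstate the change after about 24 h of drug.

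The size is unknown. The fractions tabulated above follow from assumed shares and do not estimate what this trial will show; nothing in the documents says that the row will consist mainly of short infusions. That the row understates the change rests on effects growing with infusion time, which Protocol 1.2.1 suggests but does not establish for these patients. This is a modest, cheap correction to a table definition and not a flaw in the safety assessment as a whole.

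**What to change.** In SAP 20.1.2, define the 24-hour window as ≥12 to <36 h, matching the 48- and 72-hour windows. Report termination samples from infusions under 12 h in a separate row, labelled as end of infusion with less than 12 h of treatment. Amend the time points in SAP 11.2.2 to match. For every laboratory row give n, median infusion duration and total dose; SAP Section 8 already derives duration and dose, so no new data or visits are needed.

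Costs:
- One more row, and a smaller n at 24 h. If 75% of patients had infusions under 12 h (an assumption) and all 80 gave a value, 80 × 0.25 = 20 would remain at 24 h, or 20 × 0.25 = 5 per cohort of 20 if spread evenly. Cells by cohort may be too small for more than a listing.
- Termination samples from infusions of 12 to 23 h would still be pooled with 24-hour samples. A later cut would separate them, but would break the match with the other windows and shrink the row further. Showing median duration per row lets the reader judge what remains.
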